7.1 Variables

The primary safety and tolerability variables are adverse events, vital signs (blood pressure, pulse rate, body temperature), ECG intervals, laboratory measurements, as well as subject demographics, baseline characteristics, and treatment information.

7.2 Descriptive analyses

Subject demographics and other baseline characteristics

All data for background and demographic variables will be listed by part, treatment group and subject. Summary statistics will be provided by part and treatment group.

Relevant medical history, current medical conditions, results of laboratory screens, drug tests and any other relevant information will be listed by part, treatment group and subject.

Treatment

Data for study drug administration (rescue medication) and concomitant therapies will be listed by part, treatment group and subject.

Vital signs

All vital signs data will be listed by treatment, subject, and visit/time and if ranges are available abnormalities (and relevant orthostatic changes) will be flagged. Summary statistics will be provided by part, treatment and visit/time.

ECG evaluations

All ECG data will be listed by treatment, subject and visit/time, abnormalities will be flagged. Summary statistics will be provided by part, treatment and visit/time.

Clinical laboratory evaluations

All laboratory data will be listed by treatment, subject, and visit/time and if normal ranges are available abnormalities will be flagged. A separate listing is provided presenting all parameters in a subject with any abnormal values. Summary statistics will be provided by part, treatment and visit/time.

Local tolerance at infusion site

Local tolerance at infusion site will be summarized by part and treatment group.

Adverse events

All information obtained on adverse events will be displayed by part, treatment and subject.

The number and percentage of subjects with adverse events will be tabulated by system organ class and preferred term with a breakdown by treatment, and separately by preferred term and treatment. A subject with multiple adverse events within a system organ class is only counted once towards the total of this system organ class and treatment.

The number and percentage of subjects with adverse events by maximum severity of adverse events will be tabulated by system organ class and preferred term with a breakdown by treatment.

The number and percentage of subjects with adverse events classified as related to study drug will be tabulated by system organ class and preferred term with a breakdown by treatment.

For the legal requirements of ClinicalTrials.gov and EudraCT, two required tables on all <on-treatment/treatment emergent> adverse events which are not serious adverse events and on all <on-treatment/treatment emergent> serious adverse events and SAE suspected to be related to

study treatment will be provided by system organ class and preferred term on the safety set population.

If for a same subject, several consecutive AEs (irrespective of study treatment causality, seriousness and severity) occurred with the same SOC and PT:

- a single occurrence will be counted if there is ≤ 1 day gap between the end date of the preceding AE and the start date of the consecutive AE
- more than one occurrence will be counted if there is > 1 day gap between the end date of the preceding AE and the start date of the consecutive AE.

For occurrence, the presence of at least one SAE / SAE suspected to be related to study treatment / non SAE has to be checked in a block e.g., among AE's in a ≤ 1 day gap block, if at least one SAE is occurring, then one occurrence is calculated for that SAE.

The number of deaths resulting from SAEs suspected to be related to study treatment and SAEs irrespective of study treatment relationship will be provided by SOC and PT.

Holter ECG data analysis

The relationship between change from baseline in time-matched QTcF and KAE609 plasma concentration will be explored using linear mixed effects modeling. Other ECG parameters (QT, QTcB, HR, PR interval and QRS) will be summarized. Data from the SAD and MAD parts of the study will be pooled for this assessment. The change from baseline in QTcF will be the dependent variable in the model, KAE609 plasma concentration will be a covariate, and time a categorical variable. A random intercept for each subject will be specified. Placebo subjects will be included in the analysis with a plasma concentration of 0. The placebo-corrected change from baseline in QTcF and the two-sided 90% confidence interval will be extracted from the model at the geometric mean maximum plasma concentration for each treatment.

A plot of raw QTcF change vs KAE609 plasma concentration will be presented together with the estimated slope and 90% Confidence Interval (CI) from the statistical model.

The analysis results for categorical outliers and T-wave morphology will be summarized in frequency tables with counts and percentages for both number of subjects and number of timepoints. For categorical outliers, the number of subjects (%) and timepoints will be determined by treatment group for the following:

- increase in QTcF from baseline of > 30 ms and > 60 ms
- absolute QTcF values > 500 ms
- PR change from baseline $> 25\%$ increase resulting in PR > 220 ms
- QRS change from baseline $> 25\%$ increase resulting in QRS > 120 ms
- heart rate change from baseline $> 25\%$ decrease resulting in heart rate < 50 beats per minute
- heart rate change from baseline $> 25\%$ increase resulting in a heart rate > 100 beats per minute

For T-wave morphology, the analysis will be focused on the treatment emergent changes. A cardiac safety report will be prepared separately.

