4.1 Rationale for study design

This is the first clinical study for KAE609 administered iv with the purpose of establishing safety, tolerability and pharmacokinetics in healthy subjects. The rationale for key design elements in this study include:

- **Healthy subjects:** Enrolling healthy subjects was chosen to reduce the risk of introducing confounding variables and to minimize the risk and severity of adverse events. This minimizes any underlying disease-related findings that may confound data interpretation that may exist, especially regarding transaminase elevations, which have been seen in patients with uncomplicated malaria treated with KAE609 and can be present in patients with severe malaria.
- **Randomization:** Helps to avoid possible bias in the selection and allocation of subjects.
- **Placebo comparator:** Use of a placebo helps assess if any safety or tolerability findings should be attributed to KAE609 and helps to maintain study blinding.
- **Blinding:** Blinding of subjects with limited un-blinding of investigators and sponsor minimizes bias in the conduct of the study. The Sponsor's clinical trial team will be blinded. Representatives of the Sponsor, such as the Translational Medicine Expert, may be only unblinded to facilitate safety-related decisions. Limited un-blinding of the investigators and sponsor (e.g., at the time of dose-escalation review) will be allowed if needed to help with safety-related decisions. The pharmacist at the CRO who prepares the injections will be unblinded.
- **Sequential cohorts:** This allows for an adequate safety and tolerability assessment prior to the initiation of each ascending dose.
- **Sentinel dosing:** No sentinel dosing is planned for this study. The predicted toxicities are monitorable and reversible. There is no expected effect on QT and no CNS toxicities expected in this study. A QT potential risk was seen in the hERG assay but no effect of oral KAE609 on QTcF has been observed in healthy subject or patient studies so far. Sentinel dosing is not likely to reduce the risk in this study.
- **Domiciliation:** Subjects will be domiciled before and during dosing and after last dosing to allow for close observation of safety and tolerability, and to ensure compliance with instructions for all subjects.

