10.2 Additional Safety Monitoring

10.2.1 Liver safety monitoring

To ensure subject safety and enhance reliability in determining the hepatotoxic potential of an investigational drug, a standardized process for identification, monitoring and evaluation of liver events has to be followed.

The following two categories of abnormalities / adverse events have to be considered during the course of the study (irrespective of whether classified/reported as AE/SAE):

- Liver laboratory triggers, which will require repeated assessments of the abnormal laboratory parameter
- Liver events, which will require close observation, follow-up monitoring and completion of the standard base liver CRF pages

Please refer to [Table 16-1](#) in [Appendix 1](#) for complete definitions of liver laboratory triggers and liver events.

Every liver event defined in [Table 16-1](#) should be followed up by the investigator or designated personnel at the trial site, as summarized below. Additional details on actions required in case of liver events are outlined in [Table 16-2](#). Repeat liver chemistry tests (ALT, AST, TBL, PT/INR, ALP and G-GT) to confirm elevation.

- These liver chemistry repeats will be performed using the local laboratory. Repeated laboratory test results must be reported as appropriate.
- If the initial elevation is confirmed, close observation of the subject will be initiated, including consideration of treatment interruption if deemed appropriate.
- Discontinuation of the investigational drug (refer to the Discontinuation of study treatment section), if appropriate
- Hospitalization of the subject if appropriate
- Causality assessment of the liver event
- Thorough follow-up of the liver event should include
 - These investigations can include based on investigator's discretion: serology tests, imaging and pathology assessments, hepatologist's consultancy; obtaining more detailed history of symptoms and prior or concurrent diseases, history of concomitant drug use, exclusion of underlying liver disease

All follow-up information, and the procedures performed must be recorded as appropriate in the CRF.

Refer to the SOM for additional details.

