The analysis results for categorical outliers and T-wave morphology will be summarized in frequency tables with counts and percentages for both number of subjects and number of timepoints. For categorical outliers, the number of subjects (%) and timepoints will be determined by treatment group for the following:

- increase in QTcF from baseline of > 30 msec and > 60 msec
- absolute QTcF values > 500 msec
- PR change from baseline > 25% increase resulting in PR > 220 msec
- QRS change from baseline > 25% increase resulting in QRS > 120 msec
- heart rate change from baseline > 25% decrease resulting in heart rate < 50 beats per minute
- heart rate change from baseline > 25% increase resulting in a heart rate > 100 beats per minute

For T-wave morphology, the analysis will be focused on the treatment emergent changes.

Clinical laboratory evaluations

If normal ranges are available, laboratory data abnormalities will be flagged and will be listed by part, treatment group, subject and visit/time. Summary statistics may be provided by part, treatment group and visit/time.

Individual profile plots of laboratory data (e.g. sodium, potassium, calcium, AST and ALT) will be provided. Graphical summary of these laboratory parameters will also be provided by part and treatment group.

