16.2 Appendix 2: Specific Renal Alert Criteria and Actions and Event Follow-up

Table 16-3 Specific Renal Alert Criteria and Actions

Serum Event	
Serum creatinine increase 25 – 49% compared to baseline	Confirm 25% increase after 24-48h Follow up within 2-5 days
Acute Kidney Injury: Serum creatinine increase ³ 50% compared to baseline	Follow up within 24-48h if possible Consider study treatment interruption Consider patient hospitalization /specialized treatment
Urine Event	
New dipstick proteinuria ≥1+	Confirm value after 24-48h
Albumin- or Protein-creatinine ratio increase ≥2-fold	Perform urine microscopy Consider study treatment interruption / or discontinuation
Albumin-creatinine ratio (ACR) ≥30 mg/g or ≥3 mg/mmol; Protein-creatinine ratio (PCR) ≥150 mg/g or >15 mg/mmol	
New dipstick glycosuria ≥1+ not due to diabetes	Blood glucose (fasting) Perform serum creatinine, ACR
New dipstick hematuria ≥1+ not due to trauma	Urine sediment microscopy Perform serum creatinine, ACR
For all renal events:	
Document contributing factors in the CRF: co-medication, other co-morbid conditions, and additional diagnostic procedures performed	
Monitor patient regularly (frequency at investigator's discretion) until either:	
Event resolution: sCr within 10% of baseline or protein-creatinine ratio within 50% of baseline, or	
Event stabilization: sCr level with ±10% variability over last 6 months or protein-creatinine ratio stabilization at a new level with ±50% variability over last 6 months.

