7.3 Graphical presentation

Boxplots to visualize trends in longitudinal safety data (vitals, ECG, lab parameter) will be created.

8 Statistical methods for biomarker data

Not applicable.

9 Exploratory objectives

Commercially Confidential Information

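### Subjects who meet the protocol's laboratory liver and creatinine alert criteria are not counted by treatment, and the normal-range flag is on the wrong scale for the creatinine alerts

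*SAP*

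**What the plan says.** **Planned laboratory analysis.** SAP 7.2 states: "All laboratory data will be listed by treatment, subject, and visit/time and if normal ranges are available abnormalities will be flagged". It adds: "A separate listing is provided presenting all parameters in a subject with any abnormal values". Summary statistics by part, treatment and visit follow, and SAP 7.3 adds: "Boxplots to visualize trends in longitudinal safety data (vitals, ECG, lab parameter) will be created". Protocol 12.4.2 has the same kind of flag: "If normal ranges are available, laboratory data abnormalities will be flagged and will be listed by part, treatment group, subject and visit/time". It also promises plots: "Individual profile plots of laboratory data (e.g. sodium, potassium, calcium, AST and ALT) will be provided", with graphical summaries by part and treatment group. None of these laboratory paragraphs is redacted.

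**Alert criteria.** Protocol Table 16-1 defines liver triggers and liver events, mostly as multiples of ULN, some combining ALT/AST with bilirubin or INR. Table 16-2 adds a tier above 8 x ULN. Table 16-3 defines creatinine alerts relative to the subject's own baseline. The lower tier is "Serum creatinine increase 25 – 49% compared to baseline"; a rise of 50% or more is labelled acute kidney injury (the symbol before 50% is read as a PDF rendering of ≥). Protocol 10.2.1 asks that liver triggers and events be considered "irrespective of whether classified/reported as AE/SAE".

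**Context.** Protocol 4.1 explains the choice of healthy subjects partly by "transaminase elevations, which have been seen in patients with uncomplicated malaria treated with KAE609".

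**The concern.** The protocol sets out graded laboratory criteria, and the visible analysis uses none of them. A reader of the study report would find no table showing how many KAE609 and how many placebo subjects met a laboratory liver trigger, a laboratory liver event or a creatinine alert. For transaminases this sits badly with the design, since healthy volunteers were chosen partly so that such elevations could be read without disease confounding.

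For creatinine there is a second problem. The alert is a change from baseline, while the flag is a comparison with the normal range. A subject can meet the alert and carry no flag. That subject would also be missing from the second listing unless some other value was abnormal.

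**Working it through.** **1. The plan's own figure.** Protocol Table 12-2 gives the chance of seeing affected subjects among 6 on active treatment. At a rate of 1 in 5, P(none) = 0.8^6 = 26.2%, P(at least 1) = 73.8% and P(at least 2) = 34.5%, against the stated 26%, 74% and 34%. All other cells reproduce too. The point does not depend on this table, but the table shows that the study's own yardstick is the number of affected subjects.

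**2. What each planned output can show.**
- Range flag: separates inside from outside the range. ALT at 1.1 x ULN and at 8 x ULN both count as abnormal.
- By-visit summaries and boxplots: describe one parameter at one visit. They do not count subjects against a criterion or join ALT with bilirubin or INR in one subject.
- Second listing: puts a subject's parameters side by side, but is not a count.
- Profile plots: AST and ALT are named examples; creatinine is not.
- AE tables: count subjects by system organ class, preferred term and treatment. Under Protocol 10.1.1 a laboratory value enters only if it causes signs or symptoms, is judged clinically significant or needs therapy.
- ECG, for contrast: Protocol 12.4.2 and SAP 7.2 count subjects by treatment group at fixed QTcF, PR, QRS and heart-rate thresholds, several of them percentage changes from baseline.

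**3. Creatinine: flag against alert.** Let k be the fold rise from baseline. The value is not flagged high when baseline x k ≤ ULN, that is, when baseline ≤ ULN/k.
- Rise of exactly 25%: 1/1.25 = 0.80 x ULN.
- Rise of exactly 50%: 1/1.5 = 0.667 x ULN.
- Rise of exactly 100%: 1/2 = 0.50 x ULN.

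The limit falls as the rise grows. These limits hold for any ULN.

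**4. How common are such baselines?** The documents give neither a ULN nor a baseline distribution. As an illustration only, assume the normal range is mean ± 1.96 SD of healthy values, with r = lower limit/ULN between 0.5 and 0.7. In units of ULN, mean = (1 + r)/2 and SD = (1 − r)/(2 x 1.96). The share of baselines at or below 1/k is Φ((1/k − mean)/SD).
- r = 0.5 (mean 0.75, SD 0.128): 65% for k = 1.25; 26% for k = 1.5.
- r = 0.6 (mean 0.80, SD 0.102): 50% and 10%.
- r = 0.7 (mean 0.85, SD 0.077): 26% and 1%.

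These are shares of baselines from which such a rise would go unflagged. They are not the frequency of the rise itself.

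**The case against.** **The plan has more than a flag.** A reader might infer that laboratory safety rests on the flag and visit summaries alone, or that alerts are never counted. The documents do not support either. Plots and a per-subject listing are planned. Jaundice and AEs suggestive of liver toxicity are Table 16-1 events that are AEs by definition, so they are tabulated by treatment.

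**There is a baseline-relative route to an AE.** Protocol 10.1.1 requires clinically significant values to be sought partly through significant changes from baseline, and Protocol 8.4.1 requires abnormal results to be assessed as possible AEs. A within-range creatinine rise can therefore reach the AE tables. This stands, but it rests on the investigator's judgement. What remains uncounted is threshold crossings not reported as AEs, a group whose size is unknown.

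**The appendices are site follow-up rules.** The instruction to consider liver findings regardless of AE status governs handling during the study, and Protocol 12.4.2 promises no criterion table. The SAP therefore does not contradict the protocol. With 6 active subjects per cohort, the ULN-based criteria could also be counted by hand from the listings. Both points stand. However, the same cohort sizes did not stop the plan from tabulating ECG outliers.

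**Limits of what can be seen.** Other reporting documents may exist, and parts of the risk section are redacted, so it cannot be said that transaminase elevation is the only signal. Nor do the documents say how unscheduled repeat tests enter the summaries; a loss of peak values there would be inference.

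**Conclusion.** The concern holds as an analysis gap for part of the primary endpoint. No visible passage plans a by-treatment count of subjects meeting the laboratory-based criteria of Tables 16-1 and 16-2 or the creatinine criteria of Table 16-3. Liver crossings would be flagged but neither graded nor counted. Creatinine alerts can escape the flag altogether.

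The size is exact as algebra and unknown as frequency: the limits are 0.80 x ULN for a rise of exactly 25% and 0.667 x ULN for exactly 50%. Two stronger readings are tempting. One is that any rise of 50% or more escapes when baseline is at or below 0.667 x ULN. It does not: a 60% rise from that limit gives 1.6 x 0.667 = 1.07 x ULN and is flagged. The other is that subjects are unprotected. The documents do not support this either: all values are listed, and the site actions in Tables 16-2 and 16-3 apply whatever the analysis does.

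The point covers creatinine, not the urine criteria in Table 16-3.

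**What to change.** In SAP 7.2, under clinical laboratory evaluations:

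1. Add one table by part and treatment group, with placebo pooled within part as in Protocol 12.1. Give the number and percentage of subjects whose worst post-dose value meets each existing criterion: ALT/AST > 3 to ≤ 5, > 5 and > 8 x ULN; bilirubin > 1.5 to ≤ 2 and > 2 x ULN; ALP > 2 x ULN; the combined ALT/AST criteria with bilirubin (and its ALP condition) and with INR; and each creatinine category of Table 16-3. Count irrespective of AE reporting, include scheduled and unscheduled tests, and label the table as worst value at any time. State how the components of a combined criterion are matched in time.
2. Add a baseline-relative creatinine flag to the laboratory listing, next to the normal-range flag.

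The cost is SAP wording, one or two extra tables and one derived flag. Protocol Table 8-4 already includes every analyte needed. The small downside is that unscheduled repeats follow abnormal values, hence the label. The thresholds are used unchanged, and no clinical management rule is altered.

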8.4.3 Holter ECG Monitoring

25-hour Holter monitoring will be conducted on specified days to collect ECG data for QTcF assessment. These data will not immediately be visible to the site investigator and staff. The Holter recordings will be transmitted to the selected ECG core laboratory for analysis. ECG extractions for QTcF analysis will be taken at the same nominal timepoints as the PK draws. All ECGs will be measured after a 10 min rest in the supine position prior to the PK draws.

In Part A, continuous 12 lead ECG Holter monitoring will be performed for 25 hours on Day 1 from 1 hour pre-dose through 24 hours post-dose.

In Part B, continuous 12 lead ECG Holter monitoring will be performed for 24 hours on Days 1 and 5 from 1 hour pre-dose through 24 hours post-dose.

Full details of all procedures relating to the ECG collection are contained in the SOM and/or Holter monitoring manual.

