12.4.2 Statistical model, hypothesis, and method of analysis

For all safety analyses, the safety set will be used. All listings and tables will be presented by treatment group. Graphical representations of the safety data may be produced.

Adverse events

All information obtained on adverse events will be displayed by part, treatment group and subject. The number and percent of patients with adverse events will be tabulated by system organ class and preferred term with a breakdown by treatment group. A subject with multiple adverse events within a system organ class is only counted once towards the total of the system organ class. Separate tables and listings will present adverse event severity (CTCAE grade) and relationship to study treatment.

The number (and percent) of subjects with adverse events of infusion site reaction may be summarized by treatment group.

Vital signs

If normal ranges are available, vital signs abnormalities (and relevant orthostatic changes) will be flagged and will be listed by part, subject and visit/time. Summary statistics may be provided by part, treatment group and visit/time.

ECG evaluations

Abnormal ECG data will be flagged and will be listed by part, treatment group, subject and visit/time. Summary statistics may be provided by part, treatment group and visit/time.

Holter ECG data analysis

The relationship between change from baseline in time-matched QTcF and KAE609 plasma concentration will be explored using linear mixed effects modeling. Other ECG parameters (QT, QTcB, HR, PR interval and QRS) will be summarized. Data from the SAD and MAD parts of the study will be pooled for this assessment. The change from baseline in QTcF will be the dependent variable in the model, KAE609 plasma concentration will be a covariate, and time a categorical variable. A random intercept for each subject will be specified. Placebo subjects will be included in the analysis with a plasma concentration of 0. The placebo-corrected change from baseline in QTcF and the two-sided 90% confidence interval will be extracted from the model at the geometric mean maximum plasma concentration for each treatment.

A plot of raw QTcF change vs KAE609 plasma concentration will be presented together with the estimated slope and 90% Confidence Interval (CI) from the statistical model.

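### The concentration-QTcF model omits the subject's baseline QTcF as a covariate, and neither document says which baseline serves the Day 5 Holter

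*SAP*

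**What the plan says.** The Holter analysis has the same wording in SAP 7.2 and Protocol 12.4.2. Its purpose is given as: "The relationship between change from baseline in time-matched QTcF and KAE609 plasma concentration will be explored using linear mixed effects modeling". The model is then set out: "The change from baseline in QTcF will be the dependent variable in the model, KAE609 plasma concentration will be a covariate". Time enters as a categorical variable, placebo subjects enter at concentration zero, and "A random intercept for each subject will be specified". Both parts go into one fit: "Data from the SAD and MAD parts of the study will be pooled for this assessment". For the placebo-corrected change, "the two-sided 90% confidence interval will be extracted from the model at the geometric mean maximum plasma concentration for each treatment". No treatment term and no baseline QTcF term is listed.

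Protocol 8.4.3 fixes the recordings. In Part A, "Holter monitoring will be performed for 25 hours on Day 1 from 1 hour pre-dose through 24 hours post-dose"; in Part B the same window applies on Days 1 and 5. It also says that QTcF is extracted at the nominal PK times. Table 8-1 shows a Baseline visit on Day -1 with a standard ECG (in triplicate, per its footnote), but no Holter that day.

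None of the text available defines baseline for this model: whether it is the Day -1 ECG or the Day 1 pre-dose Holter, how many extractions are averaged, or what serves Day 5. The same undefined baseline feeds the counts of QTcF increases above 30 and 60 ms.

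**The concern.** There are two separate issues.

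First, a change score carries the measurement error of its own baseline into every post-dose value of that subject. Observed baseline QTcF predicts part of that error, so leaving it out gives away some precision at no saving.

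Second, Part B has two Holter recordings, each with its own pre-dose hour. Taking each recording's own pre-dose hour as its baseline is a choice that the text leaves open. On Day 5 that hour comes after four daily doses. Any QTcF effect still present would be subtracted from the outcome while the concentration on the other side of the model stays high. As no treatment term is listed, the placebo-corrected estimate is the slope times the geometric mean Cmax. A proportional loss in slope therefore passes in full into the reported estimate and its 90% interval, in the direction of no QT effect.

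QTcF is named within the primary safety endpoint. Protocol 6.4 gives the statistician and programmers access to treatment assignments from study start, so the rule is better fixed in advance.

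**Working it through.** Neither document gives a figure for this analysis that could be reproduced. The Part A recording length agrees with its window (1 + 24 = 25 h).

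**1. Baseline covariate.** Let a subject's true drug-free QTcF be m (between-subject SD s_b), the observed baseline B = m + e (error SD s_e), and a post-dose value m + slope × C + noise. The change is slope × C + noise − e. The term m cancels; −e is shared by all of the subject's changes and becomes the random intercept. The share of its variance that B explains is

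L = s_e² / (s_b² + s_e²).

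Treatment assignment within a cohort is random, so adding B leaves the slope's expectation unchanged. In this set-up the standard error falls by at most 1 − √(1 − L). That ceiling applies to between-subject information only; within-subject information gains nothing.

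- Assumed s_b = 15 ms, s_e = 5 ms: L = 25 / (225 + 25) = 0.10; ceiling 1 − √0.90 = 5.1%.
- A gain of 4% needs L of at least 1 − 0.96² = 0.078; a gain of 7% needs at least 1 − 0.93² = 0.135.

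An illustrative simulation of the SAP model gave a gain of about 4-7% with an unbiased slope. Repeating the calculation with SDs of 15 and 5 ms gave a gain below 4%. The direction is secure, but the size depends on how noisy a single baseline is relative to the spread between subjects.

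**2. Carry-over into the Day 5 pre-dose hour.** The documents give no half-life, so T is assumed. With one compartment and q24h dosing, r = 2^(−24/T), S = r + r² + r³ + r⁴ after four doses, and trough/peak on Day 5 = S / (1 + S).

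| Assumed T | r | S | Trough/peak |
|---|---|---|---|
| 6 h | 0.0625 | 0.067 | 6% |
| 12 h | 0.25 | 0.332 | 25% |
| 24 h | 0.50 | 0.938 | 48% |
| 36 h | 0.630 | 1.434 | 59% |
| 48 h | 0.707 | 1.811 | 64% |

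Under a linear effect, that share of the Day 5 peak effect is removed by a Day 5 pre-dose baseline.

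**3. Effect on the pooled slope.** The SAP model was simulated with the planned cohort sizes, illustrative relative doses in Part A (actual levels are redacted), residual SD 6 ms, baseline error SD 5 ms, a true slope of 10, 60 runs per case, and time coded by nominal time only. Simulation error is about 0.1-0.2.

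| Assumed T | Day 1 pre-dose baseline for both days | Own pre-dose baseline on Day 5 |
|---|---|---|
| 6 h | 9.7 | 9.6 |
| 12 h | 9.8 | 8.1 |
| 24 h | 10.1 | 3.6 |
| 48 h | 10.0 | 0.8 |

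A second simulation, with other assumed variances and doses, gave 9.8-10.3 with the Day 1 baseline. With the Day 5 baseline it gave 9.8, 9.0, 5.2 and 1.5 at the same half-lives, or 9.8, 9.0, 6.6 and 3.7 with time coded as day by nominal time. The size moves with the assumptions; the direction does not.

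**The case against.** A Day 5 pre-dose baseline is hypothetical. Elsewhere the protocol uses baseline as a single pre-treatment reference: a named Day -1 visit in Table 8-1, endpoints assessed from baseline to end of study in 12.4.1, and a contrast between baseline and the previous visit in 10.1.1. On that usage the open choice is between two drug-free values. The Part B schedule grid is not in the text, some Table 8-1 footnotes are redacted, and the Holter manual or the separate cardiac safety report may hold a rule. Only 12 of 42 planned active subjects (2×6 of 5×6 + 2×6) have Day 5 data. Dosing is a short bolus or infusion, so any distribution phase puts the trough/peak ratio below the one-compartment figure for the same terminal half-life. Protocol 4.1 mentions a hERG signal but also says that no QTcF effect was seen with oral dosing. The model is exploratory, and the QTcF stopping rule does not use it.

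All of this stands, and it limits the second issue to an unstated rule with a possible bias. It does not answer the first: the covariate's absence is visible in the stated model, and including it costs nothing.

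A reader might also infer that the schedule cannot supply time-matched QTcF, because no drug-free Holter day exists. If *time-matched* described the baseline, only one of eight Part A post-dose PK times (24 h; the others are 2, 10 and 30 min and 1, 3, 6 and 12 h) would have a drug-free Holter value at the same clock time. The documents do not support that reading. Protocol 8.4.3 takes QTcF at the PK times, so the phrase reads naturally as QTcF matched to concentration, which the schedule does supply.

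**Conclusion.** The point holds as a modest improvement to the model plus a missing definition. The model should carry baseline QTcF. The expected gain is a few per cent in the slope's standard error (about 4-7% in one illustrative simulation, less if baseline error is small relative to between-subject spread).

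The Day 5 baseline should be named, because one reading that the text permits would bias the slope toward zero. That bias is negligible at an assumed half-life of 6 h and potentially large at 24 h or more. The trough/peak shares are upper bounds for a given terminal half-life, and the half-life itself is not in the documents, so no single size can be claimed. It would be wrong to conclude that the plan uses an on-drug baseline, or that the planned analysis is infeasible; neither is stated.

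**What to change.** In SAP 7.2, and in Protocol 12.4.2 if it is amended:

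1. Add each subject's centred baseline QTcF as a covariate.
2. Define one drug-free baseline, the Day 1 pre-dose Holter QTcF, for Days 1 and 5 and for the categories above 30 and 60 ms. Average it if several extractions are taken; Part A shows one pre-dose PK time, so the SAP should say how many there are.
3. Code time as day by nominal time, so that placebo subjects absorb any shift between Day 1 and Day 5.
4. State that *time-matched* means QTcF extractions matched to PK sampling times.

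The cost is wording only, using data already collected. A Day 1 baseline does not remove each subject's own variation between the two days, and day-specific time uses a few more degrees of freedom. If the Holter manual or the cardiac report plan already fixes the baseline, a cross-reference covers item 2.
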